4.2 Selection of the study population

4.2.1 Study population and justification of choice of gender

Patients with locally advanced unresectable esophageal cancer are eligible for this study if all of the following criteria are fulfilled and the patients have provided written informed consent. There is no preferred enrolment of men or women within this study. However, pregnant or breast-feeding women are excluded from participation.

4.2.2 Inclusion criteria

For inclusion in the study, **all** of the following criteria must be met:

- Signed written informed consent
- Male or female between 18 and 75 years; patients > 75 years if KPS \geq 80
- Histologically proven squamous cell carcinoma or adenocarcinoma of the esophagus, which is not curatively resectable*
**resectability has to be defined and by a surgeon prior to randomisation:
The tumor is considered unresectable due to:
T-stage, N-stage, performance status/nutritional status, co-morbidity (pulmonary function, other), tumor location upper third of the esophagus, relation to other organs/structures), other reasons (please define in CRF).*
- KPS \geq 70
- Women of child-bearing potential must have a negative pregnancy test
- Adequate cardiac, pulmonary, and ear function
- Adequate bone marrow function: leucocytes \geq $3.0 \times 10^9/L$, neutrophils \geq $1.5 \times 10^9/L$, platelets \geq $100 \times 10^9/L$, hemoglobin \geq 10.0 g/dL
- Adequate liver function: Bilirubin \leq 2.0 mg/dL, SGOT, SGPT, AP, γ -GT \leq 3 x ULN
- Adequate renal function: serum creatinine \leq 1.5 mg/dL, creatinine clearance \geq 50 ml/min (calculated value according to Cockcroft-Gault equation)
- No known allergy against chimeric antibodies.
- Effective contraception for both male and female patients if the risk of conception exists

4.2.3 Exclusion criteria

Patients are not eligible for this study, if they meet **one or more** of the following exclusion criteria:

- Distant metastasis (M1b)
- Previous treatment of esophageal cancer
- Previous exposure to monoclonal antibodies and / or EGFR-targeted therapy
- Other previous malignancy with exception of a history of a previous curatively treated basal cell carcinoma of the skin or pre-invasive carcinoma of the cervix
- Serious concomitant disease or medical condition
- FEV₁ < 1,1
- Clinically relevant coronary artery disease or a history of myocardial infarction within the last 12 months or left ventricular ejection fraction (LVEF) below the institutional range of normal
- Any active dermatological condition > Grade 1
- Contraindications to receive cisplatin, 5-FU or cetuximab
- Concurrent treatment with other experimental drugs or participation in another clinical trial with any investigational drug within 30 days prior to study screening
- Pregnancy or lactation

- Known active drug abuse/alcohol abuse
- Social situations limiting the compliance with the study requirements

4.2.4 Removal of patients from the study or study treatment

Patients are free to discontinue the study at any time without giving their reason(s).

The patient must be withdrawn from study treatment in the event of any of the following:

- Withdrawal of the patient's consent
- Occurrence of an exclusion criterion which is clinically relevant and affects the patient's safety
- Occurrence of AEs, if discontinuation is desired or considered necessary by the patient and/or investigator
- Occurrence of pregnancy during treatment
- Lack of subject compliance
- A delay of treatment with cetuximab for more than 2 consecutive weeks
- Occurrence of any grade 4 toxicities related to cetuximab
- Occurrence of \geq grade 3 allergic/hypersensitivity reaction related to cetuximab
- Occurrence of disease progression

If there is a medical reason for withdrawal, the patient will remain under the supervision of the investigator until the AEs have been resolved or declined to baseline values.

If a patient has failed to attend scheduled assessments in the study, the investigator must determine the reasons and circumstances as completely and accurately as possible.

In case of premature discontinuation of the study treatment by a patient, the investigations scheduled for the last visit should be performed, if possible. In any case, the CRF section entitled "End of Treatment" must be completed.

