4.2.6 Definition of the end of treatment

Treatment of the individual patient continues until the end of treatment evaluation (i.e. 14 weeks) or until one of the criteria listed under 4.2.4 is fulfilled.

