5.4.1.1 Skin toxicities

If a subject experiences a grade 3 skin toxicity (as defined in the US National Cancer Institute's - Common Toxicity Criteria [NCI-CTC], Version 4.0), cetuximab therapy may be delayed for up to two consecutive infusions without changing the dose level. For grade 1 or 2 acne-like rash treatment with topical antibiotics (e.g. benzoylperoxide, erythromycin) or systemic antibiotics (e.g. oral tetracyclines such as doxycycline 100 mg od) should be considered. Patients with grade ≥ 3 reactions should be referred to the dermatologist for advice and management. If pruritus occurs an oral antihistamine is advised. In case of dry skin the use of emollient creams is beneficial. Fissures may occur in dry skin and topical dressings are helpful. If the toxicity resolves to grade 2 or less by the following treatment period, treatment may resume. With the second and third occurrences of grade 3 skin toxicity, cetuximab therapy may again be delayed for up to two consecutive weeks with concomitant dose reductions to 200 mg/m² and 150 mg/m², respectively. Cetuximab dose reductions are permanent. Subjects should discontinue cetuximab if more than two consecutive infusions are withheld or a fourth occurrence of a grade 3 skin toxicity occurs despite appropriate dose reduction (see figure 1).

However, if in the opinion of the investigator the discontinuation of cetuximab is considered necessary, the subject should be withdrawn immediately.

The dose of cetuximab will be adjusted for cetuximab-related grade 3 skin toxicities only. Cetuximab therapy will not be withheld for chemotherapy related toxicities. Therefore, in the event that the next infusion of chemotherapy is delayed, the subject will receive cetuximab as previously planned.

Figure 1: Treatment adjustment in the event of grade 3 skin toxicity considered to be related to cetuximab.

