5.4.1.2 Allergic/hypersensitivity reactions

In each case of allergic/hypersensitivity reaction, the investigator should implement treatment measures according to the best available medical practice. Based on previous experience with cetuximab allergic/hypersensitivity reactions, the treatment guidelines as described in Table 2 may be applicable.

Table 2 Treatment adjustment in the event of cetuximab caused allergic / hypersensitivity reaction.

CTC Grade Allergic/ Hypersensitivity Reaction	Treatment
Grade 1	Decrease the cetuximab infusion rate by 50% and monitor closely for any worsening. The total infusion time for cetuximab should not exceed 4 hours.
Grade 2	Stop cetuximab infusion. Administer bronchodilators, oxygen, etc. as medically indicated. Resume infusion at 50% of previous rate once allergic/hypersensitivity reaction has resolved or decreased to Grade 1 in severity, and monitor closely for any worsening
Grade 3 or Grade 4	Stop the cetuximab infusion immediately and disconnect infusion tubing from the subject. Administer epinephrine, broncho- dilators, antihistamines, glucocorticoids, intravenous fluids, vasopressor agents, oxygen, etc., as medically indicated. Subjects must be withdrawn immediately from the

	treatment and must not receive any further cetuximab treatment.
--	--

Re-treatment following allergic/hypersensitivity reactions:

Once a cetuximab infusion rate has been decreased due to an allergic/hypersensitivity reaction, it will remain decreased for all subsequent infusions. If the subject has a second allergic/hypersensitivity reaction with the slower infusion rate, the infusion should be stopped and the subject should be removed from the study. If a subject experiences a Grade 3 or 4-allergic/hypersensitivity reactions at any time, cetuximab should be discontinued.

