5.4.1.3 Other reasons for cetuximab discontinuation

If a subject develops an intercurrent illness (i.e., infection) that, in the opinion of the investigator mandates interruption of cetuximab therapy, that intercurrent illness must resolve within a time frame such that no more than two consecutive infusions are withheld. After the interruption of treatment, the subject will continue with a cetuximab dose of 250 mg/m² at subsequent visits or the last dose before the interruption if there have been previous dose reductions.

If therapy must be withheld for a longer period of time, the subject will be removed from the study treatment. In special cases, the investigator may request that the patient continues to receive cetuximab (the investigator must ask permission from the Investigator-Sponsor).

5.4.2 5-Fluorouracil

Toxicities solely related to chemotherapy do not lead to a dose modification or interruption of cetuximab and vice versa.

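### Read literally, 4.2.4 with 4.2.6 stops chemoradiation for cetuximab-only events where the dosing sections stop only cetuximab, and two rules take patients out of the study without clearly keeping them in survival follow-up

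*Combined protocol and SAP*

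**What the plan says.** **General rule.** Section 4.2.4 opens its list with "The patient must be withdrawn from study treatment in the event of any of the following". Three bullets concern cetuximab alone: a delay over 2 consecutive weeks, any related grade 4 toxicity, and a related hypersensitivity reaction of grade 3 or higher. Section 4.2.6 says a patient's treatment runs to the end-of-treatment evaluation "or until one of the criteria listed under 4.2.4 is fulfilled". Neither section names a component.

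**Dosing sections.** Section 5.4.1.1 says: "Subjects should discontinue cetuximab if more than two consecutive infusions are withheld". Where the investigator thinks stopping cetuximab is necessary, it adds that "the subject should be withdrawn immediately", without saying from what. In 5.4.1.2, the grade 3 or 4 row of Table 2 begins "Subjects must be withdrawn immediately from the" treatment and ends by ruling out further cetuximab. The closing sentence of 5.4.1.2, on grade 3 or 4, ends "reactions at any time, cetuximab should be discontinued". Section 5.4.2 adds: "Toxicities solely related to chemotherapy do not lead to a dose modification or interruption of cetuximab and vice versa".

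**Removal from the study.** For a second reaction at the reduced infusion rate, 5.4.1.2 says "the infusion should be stopped and the subject should be removed from the study". Section 5.4.2.1 withdraws a patient from the study when therapy is delayed for more than 2 weeks. For cisplatin, 5.4.3.1 resumes at 75% of the dose after a gap of that length.

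**Follow-up.** Section 7.3 requires end-of-treatment assessments at any premature withdrawal, and footnote 8 of the assessment schedule times follow-up from that visit. Section 8.3.4 censors survival at the last date known alive.

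**The concern.** The same cetuximab event leads to two different instructions. In arm A, cetuximab starts on day 1, and chemotherapy and radiotherapy start on day 8. Under the general rule, a patient with a grade 3 reaction to the first infusion leaves protocol treatment before any chemoradiation has been given. Under the dosing sections, the patient stops the added drug and goes on to the same chemoradiation as arm B. Sites could act differently on identical events, and the cetuximab triggers exist in arm A only.

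The second issue bears on the primary endpoint. A patient taken out of the study after toxicity or a long delay may have no 2-year survival status. Such patients are not a random subset, so early censoring of them could be informative. Section 8.1 places patients who discontinued the study because of toxicity in the per-protocol set used for the primary efficacy analysis, so their survival status is needed.

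**Working it through.** **1. Sections side by side**

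| Event | General rule | Dosing section |
|---|---|---|
| Cetuximab withheld beyond 2 weeks | 4.2.4 and 4.2.6: study treatment ends | 5.4.1.1: stop cetuximab |
| Hypersensitivity, grade 3 or higher | 4.2.4 and 4.2.6: study treatment ends | 5.4.1.2, closing sentence and end of the Table 2 row: no more cetuximab |
| Second reaction at slower rate | not listed | 5.4.1.2: out of the study |
| Therapy delayed beyond 2 weeks (both arms) | not listed | 5.4.2.1: out of the study; 5.4.3.1: cisplatin resumes at 75% |

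Study treatment is not defined. Section 4.1 uses the term after describing both arms, and 8.4 uses it for the 66 patients already randomised and treated. Arm B receives no cetuximab, so in those places the term must include chemoradiation.

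**2. The plan's own figures (Table 10)**

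Take 2 x 36 patients with 30% versus 61.73% alive at 2 years. HR = ln(0.6173)/ln(0.30) = 0.4007, as stated. Schoenfeld events at two-sided 0.05 and 80% power are 4 x (1.960 + 0.842)² / (ln 0.4007)² = 37.5, rounded up to 38, as stated. Over all nine rows the hazard ratios agree within 0.0001. The event counts agree in eight rows and differ by 1 in the ninth.

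**3. Expected grade 3/4 reactions in arm A**

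Arm size is 33 to 39 (Table 10). The rates are the protocol's own: 1% with antihistamine plus corticosteroid (2.3.2.3), 2.5% (2.3.2.4) and 3% (2.3.2.2). Expected number = rate x n; P(at least one) = 1 − (1 − rate)ⁿ.

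| Rate | Expected | P(at least one) |
|---|---|---|
| 1% | 0.33–0.39 | 0.28–0.32 |
| 2.5% | 0.83–0.98 | 0.57–0.63 |
| 3% | 0.99–1.17 | 0.63–0.70 |

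Both premedications are mandatory before the first infusion, so 1% fits best. Section 2.3.2.4 puts about 80% of all such reactions at the first infusion. If that share also holds for grade 3/4, then 0.8 x 0.33 = 0.26 to 0.8 x 1.17 = 0.94 reactions would fall before any chemoradiation.

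**4. Loss to follow-up**

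Table 10 allows about 5% loss: 0.05 x 33 = 1.65 to 0.05 x 39 = 1.95 patients per arm. One patient is 100/39 = 2.6% to 100/33 = 3.0% of an arm, so two removals in one arm use up its allowance.

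Power for 2 x 36 at HR 0.4007, with exponential survival and loss:

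| Loss over 2 years | Expected events | Power |
|---|---|---|
| 5% (plan) | 38.1 | 0.806 |
| 10% (assumed) | 37.3 | 0.798 |
| 20% (assumed) | 35.5 | 0.778 |

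**5. Patients still to be enrolled**

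Section 8.4 counts 66 treated by the end of July and expects 72 to 78 in the full analysis set. With equal allocation, (72 − 66)/2 = 3 to (78 − 66)/2 = 6 more patients enter arm A. Expected reactions among them are 0.01 x 3 = 0.03 to 0.03 x 6 = 0.18.

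**The case against.** The strongest reply is that a site managing the event would open the dosing sections, and most of these point to cetuximab alone. The Table 2 row ends by naming the drug. Section 5.4.1.3 is about stopping cetuximab; it takes the patient off study treatment, but its exception is permission to continue cetuximab, so there the term seems to mean the antibody. The synopsis lists cetuximab as investigational and the rest as concomitant. This makes the cetuximab-only reading the likely intention. It does not remove the conflict, because 4.1 and 8.4 use the same term for both arms and 4.2.4 carries no limit.

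On follow-up, a reader might infer that every patient withdrawn early is lost to the survival analysis, or that the plan censors at withdrawal. The documents do not support either. Section 7.3 with footnote 8 implies continued follow-up after withdrawal from treatment, 8.1 expects toxicity discontinuations in the primary set, and 8.3.4 has no rule that censors at withdrawal. What stands is narrower. For the two rules that say the study, no section clearly keeps the patient in survival follow-up. Section 4.2.7 offers guideline care, and 7.4 does not mention removed patients.

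A reader might also infer from 5.4.3.1 that 5-FU should restart after a long delay, as cisplatin does. That would be a new dosing policy, and nothing in the documents supports its safety.

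**Conclusion.** The point holds as a conflict of wording with a small expected effect. About 0.3 to 1.2 grade 3/4 reactions are expected in arm A, depending on which of the protocol's rates applies. Power stays near 0.8 even at an assumed 20% loss. The number of delays over 2 weeks, and of patients who would leave follow-up because of them, is not given, so that part cannot be sized.

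Toxicity-related loss of 2-year status is possible, not shown: it arises only if sites stop contact with patients removed from the study. Likewise, the loss of chemoradiation after a day-1 reaction follows from a literal reading of 4.2.4 and 4.2.6, not from an explicit instruction to stop it, and 4.2.7 would still allow guideline treatment. Severity is minor; this is a cheap improvement.

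**What to change.** 1. In 4.2.4 and 4.2.6, make the cetuximab-delay and grade 3 or higher hypersensitivity criteria lead to permanent discontinuation of cetuximab, subject to the permission in 5.4.1.3. State that 5-FU, cisplatin and radiotherapy continue under their own rules unless the investigator judges this unsafe. In the grade 4 bullet, name the components that stop.
2. In 5.4.1.2, change removal from the study to discontinuation of cetuximab. In 5.4.2.1, change withdrawal from the study to withdrawal from 5-FU. Add no 5-FU restart rule, and leave the cisplatin rule in 5.4.3.1 as it is.
3. In 7.4, state that every randomised patient who has not withdrawn consent to follow-up is followed for survival to 2 years from randomisation, whatever treatment was discontinued.

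**Cost.** Under 12.5 this needs a protocol amendment with ethics approval before implementation, and patients' consent where it affects them. It adds no patients and only a few survival-status contacts. The treatment wording reaches only patients still on treatment or yet to be enrolled. The follow-up wording helps only those who would otherwise have left the study before 2 years.

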4.2.5 Study discontinuation

The whole study may be discontinued at the discretion of the coordinating investigator (LKP) in the event of any of the following:

- Medical or ethical reasons affecting the continued performance of the study
- Difficulties in the recruitment of patients
- Occurrence of AEs unknown to date in respect of their nature, severity, and duration or the unexpected incidence of known AEs.

Safety data from the study will be reviewed by the DSMB on a regular and ongoing basis to ensure that the continuation of the study is appropriate as described in Section 10.

4.2.6 Definition of the end of treatment

Treatment of the individual patient continues until the end of treatment evaluation (i.e. 14 weeks) or until one of the criteria listed under 4.2.4 is fulfilled.

4.2.7 Plan for treatment after the end of study

Following the end of treatment evaluation or end of treatment for any other cause, patients will be treated and followed according to the guidelines of the German Cancer Society.

4.2.8 Definition of the end of study

The study terminates after the last patient has completed the 2-year Follow-up phase.

5 Treatments

5.1 Treatments administered

5.1.1 Cetuximab

5.1.1.1 Recommended materials, compatibility, storage requirements and stability

Infusion sets or syringes made of polyethylene, polyurethane, polyolefine thermoplastic, polyamide glass microfibre, polypropylene and polyvinyl chloride have been tested for compatibility with cetuximab, and are recommended for use.

Cetuximab must be stored under refrigeration at +2°C to +8°C. It may not be exposed to direct sunlight or heat. **DO NOT FREEZE CETUXIMAB.**

Cetuximab is stable, and is compatible with infusion systems made from any combination of the recommended infusion system components when administered at room temperature (up to 25°C). Preparations of cetuximab in the recommended infusion containers are chemically and physically stable for up to 48 hours at controlled room temperatures up to 25 °C. The product contains no antimicrobial agent and should be used immediately. If not used immediately, in-use storage times and conditions prior to use are the responsibility of the user. In-use storage at 2-8 °C should not exceed 24 hours, unless preparation has taken place under controlled and validated aseptic conditions. Discard any unused portion of the vial.

5.1.1.2 Instructions for use and handling

Do not mix cetuximab solution with any intravenously administered medicinal product other than a sterile 0.9 % NaCl solution. Use a separate infusion line for cetuximab infusion. For dose reduction due to adverse events, see the *section 5.4.1*. **If the patient is to receive chemotherapy on the same day, wait at least one hour after completing the cetuximab infusion.**

Preparation and Administration of the Infusion

Cetuximab solution contains no antimicrobial preservative or bacteriostatic agent. This means care must be taken to ensure aseptic handling when preparing the infusion.

There are two options:

Syringe Pump:

- Calculate the required amount of cetuximab per patient and administration (e.g., 250 mg/m² for a 2 m² patient = 500 mg cetuximab). Calculate the required amount in

volume cetuximab solution at 5 mg/mL (e.g., 500 mg cetuximab = 100 mL cetuximab 5 mg/mL)

- Draw up the volume calculated above from one or several cetuximab 5 mg/mL vials, using one or several appropriate sterile syringes attached to a suitable needle.
- Remove the needle, affix the infusion line to the first filled syringe, and prime it with cetuximab.
- Put the first filled syringe into the syringe pump and set the rate. Repeat for remaining syringes.
- Monitor the infusion rate. The calculated infusion rate must not exceed the maximum infusion rate of 10 mg/min, i.e. 120 mL/h of the ready-to-use solution.
- Use a sterile 0.9% NaCl solution to flush the line at the end of infusion.

Infusion Pump or Gravity Drip:

- Calculate the required amount of cetuximab per patient and administration (e.g., 250 mg/m² for a 2 m² patient = 500 mg cetuximab). Calculate the required amount in volume cetuximab solution at 5 mg/mL (e.g., 500 mg cetuximab = 100 mL cetuximab 5 mg/mL)
- Take an infusion bag of adequate size (e.g., 250 mL) of 0.9% NaCl solution for infusion (isotonic saline for infusion).
- Draw up the volume calculated above from the NaCl bag, using an appropriate sterile syringe attached to a suitable needle. Discard the drawn up NaCl solution.
- Draw up the volume calculated above from one or several cetuximab 5 mg/mL vials, using one or several appropriate sterile syringes attached to a suitable needle.
- Fill the calculated volume of cetuximab into the NaCl infusion bag.
- Affix the infusion line and prime it with cetuximab before starting the infusion.
- Monitor the infusion rate. The calculated infusion rate must not exceed the maximum infusion rate of 10 mg/min.
- Use a sterile 0.9% NaCl solution to flush the line at the end of infusion.

A one-hour observation period is recommended after the cetuximab infusion.

For the initial dose, the recommended infusion period is 120 minutes. For subsequent weekly doses, the recommended infusion period is 60 minutes.

The maximum infusion rate must not exceed 10 mg/min (i.e., 2 mL/min of the 5 mg/mL solution, or, after dilution of 1 part cetuximab 5 mg/mL in 4 parts 0.9%-NaCl solution (1:5 dilution) 10 mL/min = 600 mL/h).

Cetuximab must be administered under the supervision of a physician experienced in the use of antineoplastic medicinal products. Close monitoring is required during the infusion and for at least 1 hour after the end of the infusion. Availability of resuscitation equipment must be ensured.

Prior to the first infusion, patients must receive premedication with an antihistamine and glucocorticoid. This premedication is recommended prior to all subsequent infusions. Check the vital signs pre-, mid-, post- and one hour post-infusion.

Cetuximab is administered once a week for a total of 14 weeks. The initial dose is 400 mg cetuximab per m² body surface area. The subsequent weekly doses are 250 mg/m² each.

Cetuximab should always be administered prior to cisplatin and 5-FU. There must be at least one hour between the end of the cetuximab infusion and the beginning of the chemotherapy infusions.

5.1.2 5-Fluoruracil (5-FU)

The mechanism of action of 5-FU is based on its use as a “false” nucleotide in DNA synthesis. Like uracil, 5-FU is converted into its deoxymonophosphate within the cell. F-deoxy-UMP competitively inhibits the enzyme thymidilate synthetase and therefore stops DNA synthesis. Therefore, 5-FU shows maximal cytotoxic activity in the S-phase of the cell cycle.

5-FU is one of the oldest and most commonly used cytotoxic agents in the treatment of cancer. Main adverse reactions observed are myelosuppression, nausea and vomiting, mucositis and diarrhea. Following continuous infusion, hand-foot syndrome is commonly observed.

Commercially available 5-FU will be used. Investigators should refer to the respective Summary of Product Characteristics (SmPC) for complete prescription information such as dosage and administration, safety issues (warning, precautions), adverse reactions, dose modifications and omissions and storage information. Investigators should also follow institutional procedures for the administration of 5-FU.

Cetuximab should always be administered prior to 5-FU. There must be at least one hour between the end of the cetuximab infusion and the beginning of the 5-FU infusion.

5-FU will be administered as a continuous intravenous infusion on days 1-4 at the beginning of each course.

